10.5. Appendix 5: Data Display Standards & Handling Conventions

10.5.1. Reporting Process

Software	

 The currently supported versions of SAS software will be used. 	
Reporting Area	
HARP Server	: \UK1SALX00175.corpnet2.com\
HARP Compound	: \arprod\gsk3186899\mid208436\
Analysis Datasets	

 Analysis datasets will be created according to CDISC standards (SDTM IG Version 3.2 & ADaM IG Version 1.1] 	
Generation of RTF Files	

 RTF files will be generated for SAC. 	

10.5.2. Reporting Standards

General	

 The current GSK Integrated Data Standards Library (IDSL) will be applied for reporting, unless otherwise stated (IDSL Standards Location: https://spope.gsk.com/sites/IDSLLibrary/SitePages/Home.aspx): 
 4.03 to 4.23: General Principles 5.01 to 5.08: Principles Related to Data Listings 6.01 to 6.11: Principles Related to Summary Tables 7.01 to 7.13: Principles Related to Graphics Do not include subject level listings in the main body of the GSK Clinical Study Report. All subject level listings should be located in the modular appendices as ICH or non-ICH listings 	
Formats	
	
 GSK IDSL Statistical Principles (5.03 & 6.06.3) for decimal places (DP's) will be adopted for reporting of data based on the raw data collected, unless otherwise stated. Numeric data will be reported at the precision collected on the eCRF. The reported precision from non eCRF sources will follow the IDSL statistical principles as indicated below but may be adjusted to a clinically interpretable number of DP's. 
 Display all numeric variables with the same number of decimal places as the collected precision. Display minimum and maximum values with the same number of decimal places as the collected precision. Display the mean and percentiles (e.g. median, Q1, and Q3) with one additional decimal place. Display the standard deviation and standard error with two additional decimal places. Within a column, align all data values or summary statistics along the decimal point.

The reported precision for PK concentration data will be 1 decimal place but may be altered by parameter depending on the significant digits.	
Planned and Actual Time	

 Reporting for tables, figures and formal statistical analyses: 
 Planned time relative to dosing will be used in figures, summaries, statistical analyses and calculation of any derived parameters, unless otherwise stated. The impact of any major deviation from the planned assessment times and/or scheduled visit days on the analyses and interpretation of the results will be assessed as appropriate. Reporting for Data Listings: 
 Planned and actual time relative to study drug dosing will be shown in listings (Refer to IDSL Statistical Principle 5.05.1). Unscheduled or unplanned readings will be presented within the subject's listings. 	
Unscheduled Visits	

 Unscheduled visits will not be included in summary tables and figures. All unscheduled visits will be included in listings. 	
Descriptive Summary Statistics	
Continuous Data	Refer to IDSL Statistical Principle 6.06.1
Categorical Data	N, n, frequency, %
Graphical Displays	

 Refer to IDSL Statistical Principles 7.01 to 7.13. 	

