#### **9.1.5.     Clinical Safety Laboratory Assessments**

Refer to [Appendix 2](#) for the list of clinical laboratory tests to be performed and to the SoA for the timing and frequency.

- The investigator must review the laboratory report, document this review, and record any clinically relevant changes occurring during the study in the AE section of the CRF. The laboratory reports must be filed with the source documents. Clinically significant abnormal laboratory findings are those which are not associated with the underlying disease, unless judged by the investigator to be more severe than expected for the participant's condition.
- All laboratory tests with values considered clinically significantly abnormal during participation in the study should be repeated until the values return to normal or baseline or are no longer considered significantly abnormal by the investigator or medical monitor.

- If such values do not return to normal/baseline within a period of time judged reasonable by the investigator, the etiology should be identified, and the sponsor notified.
- All protocol-required laboratory assessments (including tests for urine trace proteins and safety biomarkers), as defined in [Appendix 2](#), must be conducted in accordance with the SRM and the SoA.

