10.6. Appendix 6: Derived and Transformed Data

10.6.1. General

Multiple Measurements at One Analysis Time Point

 Mean of the measurements will be calculated and used in any derivation of summary statistics but if listed, all data will be presented. Participants having both High and Low values for Normal Ranges at any post-baseline visit for safety parameters will be counted in both the High and Low categories of “Any visit post-baseline” row of related summary tables. This will also be applicable to relevant Potential Clinical Importance summary tables.
Study Day and Period Study Day

 In PART A for each period: Period Study day is calculated as the number of days from first Dose Date in the period for each subject as follows: 
 Ref Date = Missing → Period Study Day = Missing Ref Date < First Dose Date in the period → Period Study Day = Ref Date – First Dose Date Ref Date ≥ First Dose Date in the period → Period Study Day = Ref Date – First Dose Date + 1 In Part A and Part B: Study day is calculated as the number of days from First Dose Date in each Cohort for each subject as: 
 Ref Date = Missing → Study Day = Missing Ref Date < First Dose Date → Study Day = Ref Date - First Dose Date Ref Date ≥ First Dose Date → Study Day = Ref Date – (First Dose Date) + 1

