10.7. Appendix 7: Reporting Standards for Missing Data

10.7.1. Premature Withdrawals

Element	Reporting Detail
General	
 Subject study completion (i.e. as specified in the protocol) was defined as the completion of all phases of the study including the last scheduled procedure shown in SoA (Appendix 2). The end of study is defined as the date of the last visit of the last participant in the study or last scheduled procedure shown in the SoA for the last participant in the trial. Withdrawn subjects may be replaced in the study. All available data from participants who were withdrawn from the study will be listed and all available planned data will be included in summary tables and figures, unless otherwise specified.

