10.12.5. Safety Tables

Safety: Tables					
No.	Population	IDSL / Example Shell	Title	Programming Notes	Deliverable
Adverse Events (AEs)					
3.1.	Safety	AE1CP	Summary of All Adverse Events by System Organ Class and Preferred Term – Part A	ICH E3	IA, SAC
3.2.	Safety	AE1	Summary of All Adverse Events by System Organ Class and Preferred Term – Part B	ICH E3	SAC
3.3.	Safety	AE3	Summary of Common (>=5%) Adverse Events by Overall Frequency – Part A	FDAAA, EudraCT	SAC
3.4.	Safety	AE3	Summary of Common (>=5%) Adverse Events by Overall Frequency – Part B	FDAAA, EudraCT	SAC
3.5.	Safety	AE1	Summary of All Drug Related Adverse Events by System Organ Class and Preferred Term – Part A	ICH E3	SAC
3.6.	Safety	AE1	Summary of All Drug Related Adverse Events by System Organ Class and Preferred Term – Part B	ICH E3	SAC
Serious and Other Significant Adverse Events					
3.7.	Safety	AE16	Summary of Serious Adverse Events by System Organ Class and Preferred Term (Number of Subjects and Occurrences) – Part A	FDAAA, EudraCT	SAC
3.8.	Safety	AE16	Summary of Serious Adverse Events by System Organ Class and Preferred Term (Number of Subjects and Occurrences) – Part B	FDAAA, EudraCT	SAC
Laboratory: Chemistry					
3.9.	Safety	LB1	Summary of Chemistry Changes from Baseline – Part A	ICH E3	SAC
3.10.	Safety	LB1	Summary of Chemistry Changes from Baseline – Part B	ICH E3	SAC

Safety: Tables					
No.	Population	IDSL / Example Shell	Title	Programming Notes	Deliverable
3.11.	Safety	LB17	Summary of Worst-Case Chemistry Results by PCI Criteria Post-Baseline Relative to Baseline – Part A	ICH E3	SAC
3.12.	Safety	LB17	Summary of Worst-Case Chemistry Results by PCI Criteria Post-Baseline Relative to Baseline – Part B	ICH E3	SAC
Laboratory: Haematology					
3.13.	Safety	LB1	Summary of Haematology Changes from Baseline – Part A	ICH E3	SAC
3.14.	Safety	LB1	Summary of Haematology Changes from Baseline – Part B	ICH E3	SAC
3.15.	Safety	LB17	Summary of Worst-Case Haematology by PCI Criteria Post-Baseline Relative to Baseline – Part A	ICH E3	SAC
3.16.	Safety	LB17	Summary of Worst-Case Haematology by PCI Criteria Post-Baseline Relative to Baseline – Part B	ICH E3	SAC
Laboratory: Urinalysis					
3.17.	Safety	LB1	Summary of Urine Concentration Changes from Baseline – Part A	ICH E3 Includes Baseline values.	SAC
3.18.	Safety	LB1	Summary of Urine Concentration Changes from Baseline – Part B	ICH E3 Includes Baseline values.	SAC
3.19.	Safety	UR3a	Summary of Urinalysis Dipstick and Microscopy Results – Part A		SAC

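### SAP 10.5.2 keeps unscheduled visits out of every summary table, with no exception for the worst-case and abnormality-count tables, so these can understate the worst post-baseline value

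*SAP*

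**What the plan says.** SAP 10.5.2, under unscheduled visits, gives two rules: "Unscheduled visits will not be included in summary tables and figures" and "All unscheduled visits will be included in listings". The preceding block, on data listings, adds: "Unscheduled or unplanned readings will be presented within the subject's listings". SAP 10.7.1 takes the same line for withdrawn participants: "all available planned data will be included in summary tables and figures, unless otherwise specified".

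SAP 10.12.5 lists 34 safety tables. Eight of them report a worst post-baseline result, in pairs for Parts A and B: chemistry (3.11, 3.12: "Summary of Worst-Case Chemistry Results by PCI Criteria Post-Baseline Relative to Baseline"), haematology (3.15, 3.16: "Summary of Worst-Case Haematology by PCI Criteria Post-Baseline Relative to Baseline"), urinalysis (3.21, 3.22) and vital signs (3.33, 3.34). Tables 3.25 and 3.26 count hepatobiliary laboratory abnormalities. No programming note on any of these ten tables brings unscheduled values back in.

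SAP 10.6.1 covers several measurements at one analysis time point: "Mean of the measurements will be calculated and used in any derivation of summary statistics".

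Protocol 9.1.5 says: "All laboratory tests with values considered clinically significantly abnormal during participation in the study should be repeated", and this continues until they settle. Protocol 8.1.3 calls for a creatinine repeat within 24 hours once the rise exceeds 26 µmol/L, and for low phosphate to be confirmed by a repeat. Protocol section 9 allows unscheduled samples for safety reasons.

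**The concern.** Leaving unscheduled data out of by-visit means is ordinary practice, because such data come mostly from participants who already have a problem. A worst-case table has a different purpose: to show the most extreme value each participant reached after baseline. Dropping readings from a maximum or minimum can leave it unchanged or make it milder, but never more extreme. The error therefore runs one way, towards apparent safety.

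Laboratory data and vital signs are part of the primary endpoint. These tables set abnormal findings out by dose, in groups small enough for a single participant to change the picture.

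**Working it through.** The plan states no figure to reproduce. The check traces the rule through the planned displays and the assessment schedule.

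**1. Is there an exception elsewhere?** The SAP applies the sponsor's display library standards unless it states otherwise, and 10.5.2 does state otherwise. SAP 10.7.1 refers to planned data only. SAP 10.6.1 counts a participant with both high and low values after baseline in both categories, and extends this to the potential-clinical-importance (PCI) tables, but it does not say whether unscheduled visits count. No exception was found.

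**2. Do the protocol's extra readings fall off schedule?** From the schedules of activities (protocol 2.1 and 2.2), post-dose laboratory days before follow-up are:
- Part A, each period: Days 2 and 4, a gap of 2 days.
- Part B: Days 2, 4, 6, 8, 10 and 12, all gaps 2 days.

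A repeat within 24 hours of a scheduled sample therefore falls on another scheduled laboratory day in 0 of 2 cases (Part A) and 0 of 6 (Part B). In Part B, vital signs on Days 2 to 10 are pre-dose only, so a symptom-driven blood pressure later on those days is off schedule too. After a liver stopping event, protocol Appendix 6 sets repeats and weekly or twice-weekly monitoring outside the planned grid.

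**3. When does the tabulated worst case change?** The examples use phosphate, with the PCI lower limit of <0.87 mmol/L (SAP 10.8.1). All values are assumed.

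| Scheduled | Unscheduled | Worst, scheduled only | Worst, all values |
|---|---|---|---|
| 0.95, 0.90, 0.88 | 0.78 | 0.88, not flagged | 0.78, flagged |
| 0.79 | 0.74 | 0.79, flagged | 0.74, flagged |

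In the first row the count loses a case. In the second, the scheduled value already crosses the limit, so the flag stands and only the extreme is understated.

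**4. Averaging.** If a repeat were filed at the same nominal time as the first value, 10.6.1 would average the two. With assumed values 0.79 and 0.97, the mean is (0.79 + 0.97)/2 = 0.88, which is not flagged although one reading was below the limit. The SAP does not say how repeats are assigned to time points.

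**5. Size of one missed case.** Eight participants at 3:1 give 6 active per dose level. One case is 1/6 = 17%, and 0/6 if missed. The 300 mg dose is given in Cohorts 1 and 2, so up to 12 active (1/12 = 8%). Cohort 3 has up to 14, all active (1/14 = 7%).

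**The case against.** The case for leaving the text alone has real substance.

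- **The values are not lost.** All unscheduled visits are listed, and listings 44 and 45 are to show all chemistry data for a participant with any PCI value. Clinically significant laboratory changes are to be recorded as adverse events and so reach Tables 3.1 to 3.6. Liver stopping events have Tables 3.23 and 3.24. This stands, and it limits the consequence.
- **The rule says visits, not readings.** The sentence on unscheduled readings sits under listings and says only that they are listed. The SAP does not say whether a repeat taken in-house is an unscheduled visit. This also stands, but the ambiguity itself needs settling before programming, and the planned-data wording in 10.7.1 points towards exclusion.
- **The analyses are descriptive.** No hypothesis is tested. That reduces the stakes, but a table labelled worst case should still show one.

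A reader might infer three stronger things that the documents do not support:

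- **That the tables lose every confirmed stopping event.** A confirming repeat needs a first qualifying value. If that came from a scheduled sample, it stays in the table. In addition, the PCI limits are not the stopping criteria. A man whose creatinine rises from 70 to 100 µmol/L (+30, assumed values) exceeds the 26 µmol/L change criterion but not the PCI limit of >112, so he is unflagged with or without the repeat.
- **That a 24-hour repeat is always averaged with the first value.** The averaging rule covers one analysis time point, and a repeat about a day later is not clearly at that point.
- **That a withdrawn participant disappears from the safety summaries.** The adverse event and liver-event tables do not depend on visit scheduling, and withdrawals are also reported under disposition.

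**Conclusion.** The point holds within clear limits. Applied as written, SAP 10.5.2 makes the eight worst-case tables and the two hepatobiliary abnormality tables understate the worst post-baseline result whenever an off-schedule reading is more extreme than every scheduled one, or is the only abnormal one. The bias is always towards apparent safety. Where a group has 6 active participants, one such case changes the count from 1/6 to 0/6; the proportion is smaller for 300 mg and Cohort 3.

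This rests on reading unscheduled visits to include in-house repeats and symptom-driven readings, which the SAP implies but does not define, and on the table shells adding no exception of their own, since their specifications are not in the documents. How often the situation would arise cannot be estimated from the documents, and the phosphate values are illustrations only.

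**What to change.** In SAP 10.5.2, limit the exclusion of unscheduled data to by-visit summaries. State that worst-case, PCI and abnormality-count tables (3.11, 3.12, 3.15, 3.16, 3.21, 3.22, 3.25, 3.26, 3.33, 3.34) use all post-baseline values, scheduled or not, and that in-house repeats count as such values. Align the planned-data wording in 10.7.1.

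In SAP 10.6.1, state that averaging applies to protocol-planned replicates, such as the triplicate ECGs and vital signs, and that repeat values are not averaged before the worst case is taken.

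The cost is a few sentences of SAP text and a programming flag. No new data, visits or samples are needed.

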10.5.3. Reporting Standards for Pharmacokinetic

Pharmacokinetic Concentration Data	
PC Windows Non-Linear (WNL) File	PC WNL file (CSV format) for the non-compartmental analysis by Clinical Pharmacology Modelling and Simulation function will be created according to [SOP_514512]. Note: Concentration values will be imputed as per GUI_51487
Descriptive Summary Statistics, Graphical Displays and Listings	
	Refer to IDSL PK Display Standards. Refer to IDSL Statistical Principle 6.06.1. Note: Concentration values will be imputed as per GUI_51487 for descriptive summary statistics/analysis and summarized graphical displays only.
Pharmacokinetic Parameter Derivation	
PK Parameter to be Derived by Programmer	None. All PK parameters will be derived by the CPMS Pharmacokineticist.
Pharmacokinetic Parameter Data	
Is NQ impacted PK Parameters Rule Being Followed	Yes, refer to Standards for Handling NQ Impacted PK Parameters guidance.
Descriptive Summary Statistics, Graphical Displays and Listings	Refer to IDSL PK Display Standards. Log _e -transformed data: N, n, geometric mean, 95% CI of geometric mean, standard deviation (SD) of log _e transformed data and between subject

CONFIDENTIAL

208436

geometric coefficient of variation (CV_b (%)) will be reported.
 CV_b (%) = $\sqrt{(\exp(SD^2) - 1) * 100}$
[NOTE: SD = SD of \log_e transformed data]

Parameters Not Being \log_e Transformed: Tmax and T1/2.

10.6. Appendix 6: Derived and Transformed Data

10.6.1. General

Multiple Measurements at One Analysis Time Point

 Mean of the measurements will be calculated and used in any derivation of summary statistics but if listed, all data will be presented. Participants having both High and Low values for Normal Ranges at any post-baseline visit for safety parameters will be counted in both the High and Low categories of “Any visit post-baseline” row of related summary tables. This will also be applicable to relevant Potential Clinical Importance summary tables.
Study Day and Period Study Day

 In PART A for each period: Period Study day is calculated as the number of days from first Dose Date in the period for each subject as follows: 
 Ref Date = Missing → Period Study Day = Missing Ref Date < First Dose Date in the period → Period Study Day = Ref Date – First Dose Date Ref Date ≥ First Dose Date in the period → Period Study Day = Ref Date – First Dose Date + 1 In Part A and Part B: Study day is calculated as the number of days from First Dose Date in each Cohort for each subject as: 
 Ref Date = Missing → Study Day = Missing Ref Date < First Dose Date → Study Day = Ref Date - First Dose Date Ref Date ≥ First Dose Date → Study Day = Ref Date – (First Dose Date) + 1

10.6.2. Study Population

Treatment Exposure and Compliance

For Parts A and B:
 
 Treatment compliance will be calculated based on the formula: $\text{Treatment Compliance} = \frac{\text{Number of Doses taken}}{\text{Planned Treatment Duration in Days} * \text{Frequency}}$ 
where Frequency will be 1 for OD, 2 for BID or 3 for TID. Treatment compliance could be greater than 100% if there are events of overdose.
 
 Planned Treatment Duration is defined as 10 days, for each Cohort in Part B. As Part A is single dose this would be one day. Number of days of exposure to study drug will be calculated based on the formula: $\text{Duration of Exposure (in Days)} = \text{Treatment Stop Date} - \text{(Treatment Start Date)} + 1$ Participants who were randomized but did not report a treatment start date will be categorised as having zero days of exposure. 
For Part B:
 
 The cumulative dose will be based on the formula: $\text{Cumulative Dose} = \text{Sum of (Number of Days} \times \text{Total Daily Dose)}$

Treatment Exposure and Compliance

 • If there are any treatment breaks during the study, exposure data will be adjusted accordingly.
Demographics
Age

 • GSK standard IDSL algorithms will be used for calculating age where birth date will be imputed as follows: 
 ○ Any participant with a missing day will have this imputed as day '15'. ○ Any participant with a missing date and month will have this imputed as '30th June'. • Birth date will be presented in listings as 'YYYY'.
Body Mass Index (BMI)

 • Calculated as Weight (kg) / [Height (m)]²

10.6.3. Safety

Adverse Events
[AE'S OF Special Interest]

 • Stomach erosion • Adrenal insufficiency • Renal impairment (Note: Protocol defines renal stopping and withdrawal criteria which are not "renal impairment" in the strict sense)

Laboratory Parameters

 • If a laboratory value which is expected to have a numeric value for summary purposes, has a non-detectable level reported in the database, where the numeric value is missing, but typically a character value starting with '<x' or '>x' (or indicated as less than x or greater than x in the comment field) is present, the number of decimal places in the observed values will be used to determine how much to add or subtract in order to impute the corresponding numeric value. 
 ○ Example 1: 2 Decimal Places = '<x' becomes x - 0.01 ○ Example 2: 1 Decimal Places = '>x' becomes x + 0.1 ○ Example 3: 0 Decimal Places = '<x' becomes x - 1 ○ For values '<=x' or '>=x' the value itself ('x') should be imputed as the numeric value. • Renal biomarker data will be included in the final study analysis. The parameters will be corrected using the following formula, and the units are ng/mg Corrected KIM-1=8.8*Urine KIM-1(pG/mL)/Urine Creatinine (umol/L) Corrected NGAL=8800*Urine NGAL(nG/mL)/Urine Creatinine (umol/L)

10.6.4. Pharmacokinetic

PK parameters

 • The PK Population will include all subjects who undergo PK sampling and have evaluable PK concentration results. • See Section 8.1 for derived Pharmacokinetic parameters

10.7. Appendix 7: Reporting Standards for Missing Data

10.7.1. Premature Withdrawals

Element	Reporting Detail
General	
 Subject study completion (i.e. as specified in the protocol) was defined as the completion of all phases of the study including the last scheduled procedure shown in SoA (Appendix 2). The end of study is defined as the date of the last visit of the last participant in the study or last scheduled procedure shown in the SoA for the last participant in the trial. Withdrawn subjects may be replaced in the study. All available data from participants who were withdrawn from the study will be listed and all available planned data will be included in summary tables and figures, unless otherwise specified.

10.7.2. Handling of Missing Data

Element	Reporting Detail
General	
 Missing data occurs when any requested data is not provided, leading to blank fields on the collection instrument. Unless specified otherwise, 
 These data will be indicated by the use of a "blank" in subject listing displays. Unless all data for a specific visit are missing in which case the data is excluded from the table. Answers such as "Not applicable" and "Not evaluable" are not considered to be missing data and should be displayed as such. 
Missing safety data (for e.g., lab, ECG, Vitals, etc.) will not be imputed. Missing PK data may be imputed (if required) by the Estimand strategy and will be outlined in the final RAP.

Outliers	
 Any participants excluded from the summaries and/or statistical analyses will be documented along with the reason for exclusion in the clinical study report.

